2.0 Rationale and Specific Aims

Hypothesis: A 2-dose schedule of the HPV vaccine administered at 0 and 6 months to males and females 15–26 years old will elicit a non-inferior immune response compared to 3 doses administered at 0, 2, and 6 months to females and males 15–26 years old.

Aim 1: Determine if a 2-dose schedule of Gardasil 9 administered at 0 and 6 months to females 15–26 years old elicits a non-inferior type-specific antibody response to that generated in females 15–26 years old who receive the currently recommended 3-dose schedule.

Aim 2: Determine if a 2-dose schedule of Gardasil 9 administered at 0 and 6 months to males 15–26 years old elicits a non-inferior type-specific antibody response to that generated in males 15–26 years old who receive the currently recommended 3-dose schedule.

Aim 3: Evaluate the persistence of the immune response by comparing antibody levels 6 months after the last dose in (a) females 15–26 years of age receiving 2 vs. 3 doses and (b) males 15–26 years of age receiving 2 vs. 3 doses.

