9.0 Statistical Considerations

Data Analysis: We will compare the immunogenicity of the 2-dose experimental group to the 3-dose standard care group for the corresponding sex. Participants will be required to 1) have received all injections of the vaccine within the predetermined time ranges, 2) have an adequate serum sample collected at the appropriate time intervals, and 3) be seronegative at T_0 for the HPV type that will be analyzed. Results of this experiment will be analyzed using intention-to-treat analyses, as these are the standard for non-inferiority trials.

Aim 1. Determine if a 2-dose schedule of the HPV vaccine administered at 0 and 6 months to females 15–26 years old elicits a non-inferior type-specific antibody response to that generated in females 15–26 years old who receive the currently recommended 3-dose schedule.

H_a : Two-dose 9-valent HPV vaccination immunogenicity levels among females are non-inferior to 3-dose 9-valent HPV vaccination immunogenicity levels among females.

H_0 : Two-dose 9-valent HPV vaccination immunogenicity levels are inferior to 3-dose 9-valent HPV vaccination immunogenicity levels among females.

Non-inferiority of antibody GMTs at 1 month after the last dose is administered will be tested by developing 2-sided 95% confidence intervals for the ratio of GMTs drawn at T₃, as is consistent with the power analyses of non-inferiority trials in the literature.⁸ This will be equivalent to the lower bound of a 1-sided 97.5% confidence interval (1-sided test, $\alpha=0.025$). The ratio will be developed using antibody GMTs in 15–26 year old females in the 2-dose study group relative to antibody GMTs among 16–26-year-old females in the 3-dose standard care group. In order to reject the null hypothesis, the lower bound of the ratio of antibody GMTs in females who received 2 doses should be 0.5 or greater for each of the 9 vaccine types.¹⁷⁻²⁶ If inferior immunogenicity is noted for any of the 9 vaccine types for the 2-dose experimental group, then H₀ will not be rejected.

Aim 2. Determine if a 2-dose schedule of the HPV vaccine administered at 0 and 6 month to males 15–26 years old elicits a non-inferior type-specific antibody response to that generated in males 15–26 years old who receive the currently recommended 3-dose schedule.

H_a: Two-dose Gardasil 9 immunogenicity levels among males are non-inferior to 3-dose 9-valent HPV vaccine immunogenicity levels among males.

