H₀: Two-dose Gardasil 9 immunogenicity levels among males are inferior to 3-dose 9-valent HPV vaccine immunogenicity levels among males.

Non-inferiority of antibody GMTs at 1 month after the last dose is administered will be tested similar to the analysis plan presented for Aim 1. Two-sided 95% confidence intervals for the ratio of antibody GMTs drawn at T₃ will be developed. The ratio will consist of antibody

GMTs in 15–26-year-old males as compared to 15–26-year-old males in the 3-dose standard care group. In order to reject the null hypothesis, the lower bound of the 95% confidence interval for the ratio of antibody GMTs in males should be 0.5 or greater for each of the 9 vaccine-type HPVs. If inferior immunogenicity is noted for any of the 9 vaccine types, then H₀ will not be rejected.

Secondary analyses: We will also compare immunogenicity of the experimental 2-dose group in males with the immunogenicity of the 3-dose standard care group in females. This will allow us to compare the immunogenicity of the 2-dose schedule in males to that of the standard schedule in females, the population originally studied in efficacy trials.^{14,15} Non-inferiority at T₃ will be tested by constructing 2-sided 95% confidence intervals for the ratio of antibody GMTs among the 2-dose 15–26-year-old male experimental group as compared to the 3-dose 15–26-year-old female group. To determine non-inferiority between the 2 groups, the lower bound of the ratio of antibody GMTs in males should be 0.5 or greater for each of the 9 vaccine types. We will also determine whether the level of immunogenicity for each type is above naturally-acquired immunity among males at T₃.

Aim 3: Evaluate the persistence of the immune response by comparing antibody levels 6 months after the last dose in (a) females 15–26 years of age receiving 2 vs 3 doses and (b) males 15–26 years of age receiving 2 vs 3 doses.

H_a: Two-dose Gardasil 9 immunogenicity levels are non-inferior to 3-dose 9-valent HPV vaccine immunogenicity among females and males at 6 months after the last dose.

H₀: Two-dose Gardasil 9 immunogenicity levels are inferior to 3-dose 9-valent HPV vaccine immunogenicity among females and males at 6 months after the last dose.

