Non-inferiority of antibody GMTs at 6 months after T₂ will be tested by constructing two-sided 95% confidence intervals for the ratio of antibody GMTs drawn at T₄. The ratios will consist of antibody GMTs in 15–26-year-old females in the 2-dose group as compared to 15–26-year-old females in the 3-dose standard care group. Likewise, ratios of antibody GMTs in 15–26-year-old males in the 2-dose experimental group as compared to 15–26-year-old males in the 3-dose standard care group will be constructed. In order to reject the null hypothesis, the lower bound of the 95% confidence interval for the ratio of antibody GMTs in both comparisons should be 0.5 or greater for each of the Gardasil 9 types. If inferior immunogenicity is noted for any HPV type for either sex, then H₀ will not be rejected.

Sample Size Justification:

The sample size determined for this study takes into account the need to recruit a sufficient number of participants who 1) could be included in assessments for the 9 HPV types that the vaccine protects against, considering that some may have been exposed before baseline, and 2) to account for loss to follow-up. Power analysis calculations were performed using estimates from published clinical trials and HPV prevalence rates in the age groups that will be included in this study. It was estimated that up to 15% of study participants will be seropositive for 1 or more vaccine types.¹⁶ We then assumed an attrition rate of 15% at the 12-month follow-up point.

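### The sentence defining the Aim 1 ratio gives ages 16–26 for 3-dose females but 15–26 for 2-dose females, contradicting every other description of that comparison; it should read 15–26 in both arms.

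*Combined protocol and SAP*

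**What the plan says.** The Aim 1 analysis paragraph in section 9.0 builds the ratio at T₃ from two groups. The numerator is "antibody GMTs in 15–26 year old females in the 2-dose study group". The denominator is "antibody GMTs among 16–26-year-old females in the 3-dose standard care group".

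The other descriptions of the 3-dose comparator differ from that denominator:

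- Section 2.0, Aim 1: "females 15–26 years old who receive the currently recommended 3-dose schedule".
- Section 9.0, the Aim 1 statement that opens the same analysis: "generated in females 15–26 years old who receive the currently recommended 3-dose schedule".
- Section 9.0, secondary analysis (2-dose males against 3-dose females): "as compared to the 3-dose 15–26-year-old female group".
- Section 9.0, Aim 3 at T₄: "15–26-year-old females in the 2-dose group as compared to 15–26-year-old females in the 3-dose standard care group".
- Section 9.0, Aim 2, the parallel male comparison: "as compared to 15–26-year-old males in the 3-dose standard care group".

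Section 3.0 admits both sexes from age 15 to 26, and section 4.0 randomises all of them 1:1. The conditions for entering the analysis in section 9.0 are doses in window, adequate serum and seronegativity at T₀ for the type analysed. None refers to age.

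**The concern.** The sentence with the odd age range tells the analyst whose titres form the denominator of the primary female comparison. A programmer who follows it keeps 15-year-old females in the 2-dose arm and drops them from the 3-dose arm. The plan's other analysis conditions apply to both arms alike, whereas this one would act on one arm only. The arms would then differ in age by construction, and the Aim 1 comparison would no longer be between the groups as randomised. If titres at age 15 differ from those at 16–26, the GMT ratio shifts for a reason unrelated to the number of doses.

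The text also leaves two possible control groups for Aim 1. Unless this is settled beforehand, the choice could be made once T₃ titres are known. Success requires all nine types to clear 0.5, so even a small shift can decide a borderline type.

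**Working it through.** **Step 1: the text.** Of the five other statements of the comparator listed above, four concern 3-dose females and one concerns 3-dose males. All five say 15–26. Only the Aim 1 ratio sentence says 16–26, and it conflicts with the Aim 1 statement that introduces it. No rule or reason for excluding 15-year-olds appears anywhere.

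**Step 2: effect on the ratio if applied literally.** Let f be the share of 3-dose females aged 15 and k their GMT relative to 3-dose females aged 16–26. The mean log titre of the full control arm is μ + f·ln k, where μ is the mean log titre at ages 16–26. Dropping the 15-year-olds leaves μ, so the ratio is multiplied by exp(f·ln k) = k^f.

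The documents give neither f nor k. I take f = 1/12 (ages spread evenly over the twelve years 15 to 26) and vary k on both sides of 1.

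**Step 3: effect on the type I error per HPV type.** Inputs from section 9.0:

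- margin 0.5
- one-sided α 0.025
- SD 1.2 (scale not stated; taken as natural log)
- 91 evaluable per group

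I also use 144 per group, which assumes that the 800 split equally over four groups and that both 15% losses apply: 200 × 0.85 × 0.85 ≈ 144.

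Allowing for the smaller control arm:

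- SE = 1.2 × √(1/n + 1/(n(1 − f))), which is 0.182 at n = 91 and 0.145 at n = 144.
- Error at a true ratio of 0.5 = 1 − Φ(1.960 − f·ln k / SE).
- Example, k = 1.5: f·ln k = 0.4055/12 = 0.0338. At n = 91, 1 − Φ(1.960 − 0.186) = 3.8%. At n = 144, 1 − Φ(1.960 − 0.234) = 4.2%.

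| k (assumed), f = 1/12 | Ratio multiplied by | Error, n = 91 | Error, n = 144 |
|---|---|---|---|
| 0.8 | 0.982 | 2.0% | 1.8% |
| 1 | 1 | 2.5% | 2.5% |
| 1.25 | 1.019 | 3.2% | 3.4% |
| 1.5 | 1.034 | 3.8% | 4.2% |
| 2 | 1.059 | 5.0% | 5.9% |

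A larger share of 15-year-olds widens the range in both directions. At f = 0.20 the factor is 0.956 for k = 0.8 and 1.085 for k = 1.5, the latter with an error of 6.3% at n = 91.

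These are rates per type. Because all nine types must pass, the chance of wrongly concluding non-inferiority for Aim 1 cannot exceed the rate for a type whose true ratio is at the margin.

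**Step 4: precision.** Losing 1/12 of the controls costs little. At n = 91 and a true ratio of 1.0, power per type falls from 0.974 to 0.968.

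**The plan's own figure.** The plan gives no figure for this point; its 91 per group is used only as an input. The stated inputs do not reproduce 91. The formula 2 × 1.2² × (1.960 + 1.282)² / (ln 2 + ln 1.2)² gives 40 per group, or 63 with a true ratio of 1.0. The later inflation does reproduce: 91/0.85 gives 108 and 108/0.85 gives 128. The age mismatch does not depend on these figures.

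**The case against.** The strongest reply is that this is a slip of the pen. The intended comparator can be read from the Aim 1 statement, the secondary analysis and Aim 3. Aim 2 is said to be tested in a similar way to Aim 1 and uses 15–26 on both sides. A reader might infer that the sponsor has decided to drop 15-year-old controls, but the documents do not support that: one sentence says 16–26, and nothing else implements or explains it. This part of the reply stands.

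A reader might also infer that the mismatch favours non-inferiority, because the background section reports that two doses gave a sufficient response at ages 9–14. That does not carry over. The same section places everyone who starts at 15 or older in the 3-dose population, and no titres by age within 15–26 are given. A higher response at 15 is a reasonable worry but is not established; with k below 1 the shift runs against non-inferiority. Nor do the documents support a figure such as 10% for the type I error. At k = 1.5 and 144 per group, even a quarter of females aged exactly 15 gives 9.7%, and section 4.0 lists recruitment from family medicine, women's health, colleges and the community as well as paediatrics.

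The reply does not remove the need to correct the text. The range 16–26 is not self-evidently a typing error: section 7.0 reports earlier Gardasil 9 safety data in females aged 16–26, and the cited nine-valent efficacy trial enrolled women of that age. An analyst could take it as deliberate.

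**Conclusion.** The Aim 1 ratio sentence is wrong as written: its two sides have different age ranges, and it contradicts the rest of the plan. It is probably a drafting error. Applied literally, it would exclude randomised 15-year-old females from the control arm alone, and that departure from the randomised comparison holds whatever their titres are.

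Whether the ratio would be biased, in which direction and by how much cannot be determined from the documents. If ages are evenly spread, a relative titre at age 15 between 0.8 and 1.5 shifts the ratio by between −1.8% and +3.4%. The numerical effect is therefore likely to be modest, and it rests entirely on assumed values of f and k. The reason to act is that the primary comparison must be defined unambiguously before the titres are analysed.

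**What to change.** In the Aim 1 paragraph of section 9.0, change 16–26 to 15–26 in "antibody GMTs among 16–26-year-old females in the 3-dose standard care group", so that both sides of the ratio use the same age range, as in Aims 2 and 3. Do this before analysis and record it as a correction. If 16–26 was in fact intended, the plan should say so, justify it and apply it to both arms.

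The cost is a single changed number. Design, margin and sample size stay as they are. With 15–26 in both arms, the factor from Step 2 is exactly 1 and the error per type returns to 2.5%.

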10.0 Ethics and the Protection of Human Subjects

Discussion of risks and possible benefits of Gardasil 9 will be provided to the subjects and their families. Consent forms describing in detail the study interventions/products, study procedures, and risks will be given to the subject and written documentation of informed consent obtained prior to administering Gardasil 9. Consent forms will be IRB-approved and the subject will be

asked to read and review the document. Upon reviewing the document, study personnel will explain the research study to the subject and answer any questions that may arise. The subject will sign the informed consent document prior to any procedures being done specifically for the study. The subject may withdraw consent at any time throughout the course of the trial. A copy of the informed consent document will be given to subjects for their records. The rights and welfare of the subjects will be protected by emphasizing to them that the quality of their medical care will not be adversely affected if they decline to participate in this study.

The investigator will ensure that this study is conducted in full conformity with the principles set forth in The Belmont Report: Ethical Principles and Guidelines for the Protection of Human Subjects of Research of the US National Commission for the Protection of Human Subjects of Biomedical and Behavioral Research (April 18, 1979) and codified in 45 CFR Part 46 and/or the ICH E6; 62 Federal Regulations 25691 (1997).

Privacy/Confidentiality Issues

Subject confidentiality is strictly held in trust by the participating investigators, their staff, and their agents. This confidentiality is extended to cover testing of biological samples in addition to the clinical information relating to participating subjects.

The study protocol, documentation, data, and all other information generated will be held in strict confidence. No information concerning the study or the data will be released to any unauthorized third party without prior written approval of the Principal investigator.

Individuals authorized to view study records will be identified to the study subject on the informed consent but may include a study monitor or other authorized representatives of agencies that regulate research including representatives from the Office of Human Research Protections or the Institutional Review Board. Study records may also be made available for internal compliance reviews and quality assurance representatives.

These individuals may inspect all documents and records required to be maintained by the investigator, including but not limited to, medical records (office, clinic, or hospital) and pharmacy records for the subjects in this study. The clinical study site will permit access to such records.

In accordance with the Food and Drug Administration Amendment Act of 2007 (FDAAA) and The International Committee of Medical Journal Editors (ICMJE) member journals trials-registration policy as a condition for publication, this study will be registered in the public trials registry ClinicalTrials.gov, which is sponsored by the National Library of Medicine. Results will be published to ClinicalTrials.gov when available but will not identify individual subjects.

11.0 Record Retention

The investigator shall retain records required to be maintained under 21 CFR 312.62 for a period of 3 years following the date the investigation is discontinued. There will be no marketing application for a new drug as a result of this study as the intervention of study uses an FDA-approved vaccine.

Consent forms that include the HIPAA Authorization will be retained for a minimum of 3 years from the date of the authorization.

For pediatric subjects, records shall be maintained until 3 years after completion of the research.

Research records will be maintained in accordance with the current version of the Texas Health Records Table 17-III Record Retention Schedule, Human Subject Research Records and Documents.

